### 3.2.2. Secondary endpoints

Secondary endpoints are other imaging and circulating biomarkers, defined as:

- Secondary echocardiographic measurements are:
  - Left ventricular ejection fraction using Simpson's biplane method
  - Left ventricular end-diastolic volume using Simpson's biplane method
  - Left ventricular end-systolic volume using Simpson's biplane method
  - Left-ventricular end-diastolic diameter using M-mode
  - Left ventricular mass measured according ASE/EAE guidelines
  - Global and segmental radial strain rate
  - E/A wave ratio
  - E/Ea wave ratio (lateral annulus)
  - TAPSE (tricuspid annular plane systolic excursion)
  - Tricuspid annular S wave
  - Pulmonary artery systolic pressure (based on the peak tricuspid regurgitation velocity estimate and by assuming a right atrial pressure of 5 mmHg)
  - Left ventricular outflow tract diameter
  - Left ventricular outflow tract velocity time integral
  - Heart rate
  - Cardiac output measured by multiplying heart rate by stroke volume
- CT: to measure anatomical changes in coronary arteries assessed by cardiac CT occurring 24 months after RT compared with baseline before RT start.
  - Individual description of stenosis or plaques of the 15 segments of the coronary arteries; left main coronary artery (LM); left anterior descending artery (LAD), left circumflex artery (LX) and right coronary artery (RCA) and evaluation of change in CAC score.
  - The progression atherosclerosis will be defined as an increase of the number of coronary segments containing any plaque and as an increase of the calcium score, of at least 15% between baseline and 24 months after RT.
- MRI: to evaluate myocardial tissue abnormalities assessed by cardiac MRI occurring 6 to 24 months after RT compared with baseline before RT start.
  - Cardiac MRI-parameters include: morphology, function, tissue characterization by delayed enhancement and pre-/post-contrast T1 mapping (at 15 minutes).
  - The corresponding main MRI-endpoint is defined by an increase of the native mean myocardial T1 mapping value of at least 7% (*Germain et al. Clin Med Insight Cardiol 2014*)
- Circulating biomarkers: to measure temporal changes in circulating biomarkers occurring at the end of RT, 6 to 24 months after RT compared with baseline before RT start.
  - The following circulating biomarkers are assessed:

- Classical markers of cardiac injury: C-reactive protein, Troponin I, Troponin T, B-type natriuretic peptide (BNP), NT-Pro BNP, beta2-Microglobulin, Galectin 3
  - Inflammatory cytokines: IL-6, IL-8, IL-18, TNF $\alpha$
  - Endothelial activation and dysfunction: sVCAM-1, s-ICAM-1, E-Selectin, P-Selectin, vWF, PAI-1, Fibrinogen, Thrombomodulin, TGF $\beta$ 1
  - Microparticles: CD14(monocytes), CD31(endothelial), CD41(platelets), CD3(lymphocyte), CD235a(erythrocyte)
  - MicroRNAs: miR-1, miR-133, miR-208, miR-499, miR-126, miR-130, miR-145, miR-181, miR-150, miR-155, miR-223, miR-17, miR-18, miR-22, miR-34, miR-92, miR-140, miR-182, miR-199, miR-423 and miR-590.
  - circulating DNA methylation
- Endpoint are defined as a significant increase or decrease in each biomarker between time points.

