## 1. TWO-PAGE OUTLINE OF THE PROTOCOL

**1.1. Background:** Breast cancer (BC) radiotherapy (RT) leads to coincidental radiation of the heart, resulting in increased risk of a variety of heart diseases. The prevalence of BC survivors at risk of cardiac complications will gradually increase, as the incidence of BC in Europe is still rising while prognosis significantly improved over the last decades. These late cardiac complications have a major impact on quality of life and lead to subsequent morbidity and increased mortality. Therefore, identifying BC patients with the highest-risk of radiation-induced cardiac complications is crucial for developing strategies for primary and secondary prevention, which may contribute to healthy ageing. So far, little has been done on the relationship between dose distribution to different anatomical cardiac structures during RT and early cardiovascular changes that may lead to cardiac complications.

**1.2. Main study objective:** The main objective is to identify and validate the most important cardiac imaging (ECHO-ST, CTCA and MRI) and circulating biomarkers of radiation-induced cardiovascular changes arising in the first 2 years after breast cancer radiotherapy.

**1.3. Study design:** An international multicenter prospective cohort study

**1.4. Endpoints:** The primary endpoint is defined as a mean decrease in Global and Segmental Longitudinal Strain and Strain Rate (GLS/GLSR) of at least 2.5% assessed by cardiac ultrasound 6 to 24 months after RT compared to baseline.

The secondary endpoints are:

- Changes in myocardial function assessed by cardiac ultrasound 6 to 24 months after RT compared to baseline.
- Anatomical changes in coronary artery atherosclerosis (number of coronary segments containing any plaque/stenosis, and calcium score) by cardiac CT 24 months after RT compared with baseline. The endpoint is defined as 15% or greater changes.
- Myocardial changes by MRI 6 to 24 months after RT compared with baseline (morphology, function, tissue characterization by delayed enhancement and pre-/post-contrast T1 mapping). The endpoint is defined as an increase of the mean T1 mapping value of at least 7%.
- Temporal changes in circulating biomarkers at the end of RT and 6 to 24 months after RT compared with baseline. The endpoint is defined as a significant increase or decrease in each biomarker between time points.

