Cardiac computed tomography (CT) without contrast and coronary computed tomography angiography (CTCA) provides morphological information of the coronary arteries, visualization of the coronary artery anatomy, determination of plaques and stenosis of the coronary arteries, and determination of the calcium artery calcium (CAC) score. This reflects the evolution of coronary artery disease. Three studies have measured the amount of CAC in the years following RT treatment for BC. In two studies, no elevated CAC scores in BC patients were found 5 to 15.7 years after RT treatment, whereas 1 study did find an increase in CAC score depending on radiation dose to the heart. Of the studies that did not find a CAC score increase, one did not include baseline CAC scores and the other only included a relatively small number of patients, which makes it difficult to draw definitive conclusions from these two studies. In young Hodgkin's lymphoma survivors (all under 55 years) elevated CAC scores have been found in the 5 to 35 years after RT. Based on the analysis of 15 segments of coronary arteries per patient, an increase of calcified and non-calcified plaques of around 15% was observed during a 2-year follow-up. A study concerning the general population investigated CAC scores at baseline and after 10 years of follow-up. The results showed that the diagnosis of cancer and its treatments were significantly associated with the development of CAC, even after accounting for cardiac risk factors. The results of these studies suggest that RT is associated with increased CAC scores in the long term and therefore supports the hypothesis that accelerated atherosclerosis is one of the mechanisms contributing to an increase of radiotherapy induced cardiac events after cardiac irradiation.

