## 3.2. Endpoints

### 3.2.1. Primary endpoints

The primary endpoints are defined as a mean decrease in Global Longitudinal Strain or Global Longitudinal Strain Rate, determined by cardiac ECHO-ST, of at least 2.5% between baseline and 24 months after RT (*Erven et al, Int J Radiation Oncol Biol Phys, 2012; Lo et al, In J Radiation Oncol Biol Phys, 2015*).

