##### **Non inclusion criteria:**

- Male breast cancer patients
- Neoadjuvant or adjuvant chemotherapy
- M1 disease (metastatic breast cancer)
- Medical history of coronary artery disease and/or myocardial infarction and/or atrial fibrillation
- Previous thoracic or mediastinal radiation
- Contraindications to injection of iodinated contrast such as allergy or renal failure
- Pregnancy or lactation

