## **Exclusion criteria**

- Atrial fibrillation detected during electrocardiogram before radiotherapy
- Abnormal echocardiography before radiotherapy defined as: LVEF<50%; longitudinal strain  $\leq$  -16%; longitudinal strain rate  $<$ -1%, and/or abnormal wall motion
- Presence of myocardial infarction detected during MRI before radiotherapy
- CTCA or cardiac MRI results before radiotherapy requiring revascularisation

▶ See CRF ELIGIBILITY in appendix for further details

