#### *Stage I: Descriptive analysis*

Means, standard deviations, percentages, ranges and confidence intervals of 95 % are used to summarize:

- The questionnaire medical data;
- The 2D-speckle-tracking echocardiography (ECHO-ST) measurements including strain and strain rate.
- The Coronary computed tomography angiography (CT) measurements including mean number of coronary segments with plaques and/or stenosis, and CAC score (Agatston, Volume), total and per coronary artery;
- The MRI measurements include ventricular function, size of the heart chambers and wall thickness, tissue characterization by delayed enhancement and pre-/post-contrast T1 mapping of the left ventricle;
- The measurements of all biomarkers;
- Dose distribution to the several heart substructures including ventricles and coronaries arteries.

Paired non-parametric tests (Wilcoxon signed rank test to compare medians, McNemar and Bowker to compare paired proportions). The correlation between the different covariates will be investigated using the Spearman's rank correlation coefficient.

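### Does the 15% CT progression endpoint need a stated unit and a rule for women with no plaque or calcium at baseline?

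*Combined protocol and SAP*

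**What the plan says.** Section 3.2.2 defines progression of atherosclerosis on CT as "an increase of the number of coronary segments containing any plaque and as an increase of the calcium score, of at least 15" per cent, from baseline to 24 months after radiotherapy. It also lists "evaluation of change in CAC score" in its own right. The outline (section 1.4) names the segment count and the calcium score together, then adds: "The endpoint is defined as 15% or greater changes". The likely source of the threshold is in section 2.1, where "an increase of calcified and non-calcified plaques of around 15% was observed during a 2-year follow-up".

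The primary endpoint in section 3.2.1 is worded as a "mean decrease in Global Longitudinal Strain or Global Longitudinal Strain Rate, determined by cardiac ECHO-ST, of at least 2.5" per cent. Stage I of section 9.3 summarises the "mean number of coronary segments with plaques and/or stenosis" and the calcium score, and names paired non-parametric tests. Stage II fits mixed models to continuous CT measurements. Stage III speaks of a cardiac toxicity outcome without saying what it is.

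At entry, section 4 keeps out women with "Medical history of coronary artery disease and/or myocardial infarction and/or atrial fibrillation" and excludes those with "CTCA or cardiac MRI results before radiotherapy requiring revascularisation". Nothing there requires plaque or calcium at baseline.

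**The concern.** The definition leaves two things open: the unit (each woman, or the cohort mean) and whether both measures must rise or either is enough. The unit matters because women with known coronary disease are not enrolled, so some will start with no plaque segment or a calcium score of zero. If the rule is applied woman by woman, a percentage increase from zero does not exist. A first plaque or first calcium deposit, which is what the endpoint is meant to catch, would then be classified by a rule chosen after the scans were read. The reported progression rate could depend on that choice.

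Three wording differences add to the impression of looseness. Section 3.2.2 counts 15 coronary segments and the CTCA appendix 16. Section 1.4 speaks of changes and section 3.2.2 of an increase. Sections 1.4 and 9.3 mention stenosis beside plaque, while the definition in section 3.2.2 counts plaque only.

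**Working it through.** The plan gives no power, sample size or event figure for this endpoint, so there is no figure of its own to reproduce. The check covers what the 15% applies to, each candidate unit, and the effect of a zero rule.

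**What the 15% covers.** Section 1.4 puts the threshold straight after both measures, and section 2.1 attaches about 15% to plaques. Read together, it covers segments and calcium. A calcium-only reading would contradict section 1.4.

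**Cohort mean.** Percentage change = (follow-up mean − baseline mean) / baseline mean. This is defined whenever the baseline mean is above zero.
- Illustration with four women: segments 0, 0, 2, 4 become 1, 0, 2, 4. The mean goes from 6/4 = 1.5 to 7/4 = 1.75, and 0.25/1.5 = +16.7%. The segment gained from zero counts.
- With 250 women and an assumed baseline mean of 0.5, 1 or 2 segments, a 15% rise needs 0.15 × mean × 250 = 18.75, 37.5 or 75 new segments, that is 19, 38 or 75 in all.

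**Per woman.** From a baseline of k segments, a gain of g qualifies if g/k ≥ 0.15.

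| Baseline k | Smallest qualifying gain | Check |
|---|---|---|
| 0 | undefined | division by zero |
| 1 to 6 | 1 | 1/6 = 16.7% |
| 7 to 13 | 2 | 1/7 = 14.3%; 2/13 = 15.4% |
| 14 or more | none available | 1/14 = 7.1% (15 segments); 2/14 = 14.3% (16 segments) |

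The table is the same with 15 or 16 segments.

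**Effect of a zero rule on a per-woman rate.** The documents give none of these inputs. Assume a share z of women start at zero (40% to 80%), a share i of those develop calcium (5% to 20%), and half of the others rise by at least 15%.
- Zeros dropped: 50%.
- Zeros counted as not progressing: 0.5 × (1 − z), which is 30% at z = 0.4 and 10% at z = 0.8.
- Any new calcium counted: 0.5 × (1 − z) + i × z. The extremes are 0.30 + 0.20 × 0.4 = 38% and 0.10 + 0.05 × 0.8 = 14%.

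**How the gap would be filled.** The 15% rule can be written without division: follow-up greater than baseline, and at least 1.15 times baseline. Then 0 to 0 is no, 0 to 1 is yes, 6 to 7 is yes (1.15 × 6 = 6.9) and 7 to 8 is no (1.15 × 7 = 8.05). It agrees with the percentage rule at every non-zero baseline.

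**Which unit the text favours.** The primary endpoint is a mean change, the 15% in section 2.1 is reported as an observed increase in plaques, and Stage I summarises a mean number of segments. The MRI endpoint also uses a mean T1 value, but that could be a mean over one woman's myocardium, so it carries less weight. The CTCA appendix refers to scores for each patient, but that describes how readings are added up; a cohort mean starts from the same scores.

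**The case for a change.** The best case for a change is that this is the protocol's only definition of atherosclerosis progression, that the CT line lacks the word mean which the primary endpoint has, and that one sentence would settle it without new scans. Stage I also lists McNemar's test for paired proportions, which might hint at a per-woman classification. Under the assumed inputs above, the choice of zero rule moves the rate severalfold.

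Some of this stands. The unit is not stated, nor is whether both measures must rise, and a per-woman percentage has no value at zero.

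The rest is weaker. McNemar's test compares a yes/no state at two visits; a progression label from baseline to 24 months has no baseline value, so the test does not point to one. The spread of rates rests on inputs that the documents do not give and on a unit that no section adopts. It also includes two choices that defeat the purpose of the label: dropping women who develop first disease, or calling them stable. The question of both or either has little practical effect, because Stage I already summarises segments and calcium separately.

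**Conclusion.** No change to the plan is needed. The missing unit is a gap in detail that analysts would fill sensibly: report the percentage change in the cohort mean, as the surrounding text suggests, or, for a per-woman count, treat a move from zero to above zero as progression. The differences over 15 or 16 segments, change or increase, and plaque or plaque with stenosis are clerical. The first leaves the qualifying gains in the table unchanged, and the CTCA appendix has plaque and stenosis both assessed in every segment, so either count can be produced from the same readings.

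Little depends on the label. It is secondary, has no assigned test and no sample size, and is not named as the Stage III outcome. The signed rank tests and continuous mixed models use the segment counts and calcium scores themselves, where a zero is an ordinary value, and the 250 women were sized on strain.

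This conclusion assumes that no per-woman CT label is later made the toxicity outcome in Stage III. The documents do not plan that; if it were done, the zero rule would have to be fixed before modelling began.

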## **5. TRIAL DESIGN**

MEDIRAD EARLY HEART is a multicentre prospective cohort study that will include 250 female BC patients treated with post-operative RT alone after primary breast conserving surgery to assess imaging and circulating cardiac biomarkers the first 2 years following RT.

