### 7.2. Before start of treatment protocol

About 1 to 2 weeks before the start of radiotherapy, during the visit for the RT planning-CT, women agreeing to participate in the study will give their signed written informed consent form and will then be considered as included. Cardiac MRI will not be mandatory for inclusion in EARLY HEART Study (in contrast with ECHO-ST, CT and BLOOD).

► See *CRF ELIGIBILITY*, *CRF CANCER*, *CRF planned RT* and *CRF CARDIOLOGY*, in appendix for further details

From this inclusion visit on, women's follow-up protocol will be realized. Before start of RT the following interventions will have to be performed:

- Cardiac imaging:
  - An electrocardiogram to detect any arrhythmia followed by an Automated 2D-speckle-tracking echocardiography (ECHO-ST) the most commonly used modality to evaluate myocardial dysfunction and a new technique of assessing myocardial deformation;  
► See *CRF ECHO-ST* in appendix for further details
  - Computed tomography (CT) by using both low dose non enhanced and enhanced CT scans to evaluate coronary artery lesions by assessing morphological information including plaques and stenosis of the arteries, and determination of the CAC score;  
► See *CTCA PROTOCOL* and *CRF* in appendix for further details
  - Cardiac magnetic resonance imaging (MRI) for the measurement of ventricular function, size of the two heart chambers, and wall thickness; tissue characterization by delayed enhancement; and pre-/post-contrast T1 mapping mapping and pre contrast T2 mapping of the left ventricle.  
► See *MRI PROTOCOL* and *CRF* in appendix for further details
- Circulating biomarkers (BLOOD) will be based on a panel of circulating classical and novel blood-based biomarkers (see 7.5 *Blood samples for biomarkers analysis* for further details)

Furthermore, toxicity will be assessed according CTCAE 4.03 and patient rated outcome

measures. ► See *CRF TOXICITY in appendix for further details*

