### **7.5. Blood samples for biomarkers analysis**

Each patient will have 4 blood samples. For each blood sample, 30mL of blood will be collected and divided in 6 tubes of 5 mL as follows: 2 tubes heparin; 2 tubes EDTA; 2 tubes CITRATE (2 x 5ml).

Blood samples will be collected: before RT, at the end of RT, 6 months after RT and 24 months after RT. Once blood sample is collected, a standard operation procedure will be followed ► See *BLOOD PROTOCOL in appendix for further details*.

All prepared aliquots of 500 µl (approximately 30 aliquots per patient per blood sample) will be stored and freeze at –80°C in the local investigating center for a short time period of few weeks or months (depending on the capacity of storage of the local center), and then periodically sent with a medical specialized carriers to University of Bristol which is the centre for central storage of aliquots for biomarkers analysis (Workpackage 4.2.2 Preclinical and clinical identification of standard and innovative biomarkers of radiation-induced cardiovascular toxicity).

All blood samples and aliquots will be labelled using the same anonymised code assignment for patient as the one used in CRF.

Once received at University of Bristol, for each patient at each time of blood sample, 20 aliquots will be used for biomarkers analysis, the 10 remaining aliquots will enter a long term storage collection for 15 years. After 15 years, all aliquots will be destroyed except if a patient asks for early destroy of her aliquots. Aliquots of the long term storage collection could only be used in the frame of research on cardiovascular diseases.

Responsible party for EARLY HEART aliquots collection: Pr [name], Bristol Heart

Institute, School of Clinical Sciences, University of Bristol, Bristol Royal Infirmary, [name], [name], Bristol, United Kingdom.

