## Appendix

### CRF CANCER

**Inclusion Number:** .....

**Date of the visit :** .....

**Date of Birth:** .....

• **Left breast**       **Right breast**

• **Date of the surgery :** .....

• **Type of surgery :** breast conserving surgery       mastectomy

• **Axillary lymph node exploration :**

axillary sentinel lymph node biopsy       axillary lymph node dissection

• **Histology :** In situ       invasive

• **Size (mm) :** .....

• **Regional lymph nodes (N)**

**NX** (Regional lymph nodes cannot be assessed (eg, previously removed))

**N0** (No regional lymph node metastasis)

**N1** (Metastasis to movable ipsilateral level I, II axillary lymph node(s))

**N2** (Metastases in ipsilateral level I, II axillary lymph nodes that are clinically fixed or matted or in clinically detected\* ipsilateral internal mammary nodes in the *absence* of clinically evident axillary lymph node metastasis)

**N2a** (Metastases in ipsilateral level I, II axillary lymph nodes fixed to one another (matted) or to other structures)

**N2b** (Metastases only in clinically detected\* ipsilateral internal mammary nodes and in the *absence* of clinically evident level I, II axillary lymph node metastases)

**N3** (Metastases in ipsilateral infraclavicular (level III axillary) lymph node(s), with or without level I, II axillary node involvement, or in clinically detected \* ipsilateral internal mammary lymph node(s) and in the *presence* of clinically evident level I, II axillary lymph node metastasis; or metastasis in ipsilateral supraclavicular lymph node(s), with or without axillary or internal mammary lymph node involvement)

**N3a** (Metastasis in ipsilateral infraclavicular lymph node(s))

**N3b** (Metastasis in ipsilateral internal mammary lymph node(s) and axillary lymph node(s))

**N3c** (Metastasis in ipsilateral supraclavicular lymph node(s))

• **Grade :** Grade 1       Grade 2       Grade 3

• **Vascular invasion :** yes       no

• **Presence of a component in situ :** yes       no

• **Multifocality :** yes       no

• **Her-2** : negative  positive (amplification or overexpression)

• **Oestrogen Receptor**: negative  positive

• **progesterone receptor**: negative  positive

• **Menopause** : No  Yes  Since : .....

• **Hormone therapy** Yes  No

If yes, which one : Tamoxifene  Aromatase inhibitors  Others

Date of the beginning of hormone therapy : .....

• **Date of the beginning of radiotherapy** : .....

• **Irradiation volumes** :

Breast  Chest wall

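### Every blood sample is taken after breast surgery, so the blood-marker endpoint as worded cannot separate post-operative recovery from a radiation effect

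*Combined protocol and SAP*

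**What the plan says.** Section 5 describes the cohort as "treated with post-operative RT alone after primary breast conserving surgery", so surgery comes before radiotherapy in every woman. Section 7.5 fixes the sampling times: "Blood samples will be collected: before RT, at the end of RT, 6 months after RT and 24 months after RT". None is pre-operative. Under section 7.2, women are included "About 1 to 2 weeks before the start of radiotherapy, during the visit for the RT planning-CT", and the baseline procedures run from that visit until radiotherapy starts. The day of the first blood draw is not fixed more closely than that, and no section sets a minimum interval after surgery.

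The aim in section 3.2.2 is "to measure temporal changes in circulating biomarkers occurring at the end of RT, 6 to 24 months after RT compared with baseline before RT start". It is followed by the rule "Endpoint are defined as a significant increase or decrease in each biomarker between time points"; the outline (section 1.4) repeats it: "The endpoint is defined as a significant increase or decrease in each biomarker between time points". The main echocardiographic, CT and MRI endpoints each carry a size (2.5%, 15% and 7%). The blood endpoint has neither a size nor a direction.

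For analysis, Stage I of section 9.3 covers all biomarkers and lists "Paired non-parametric tests (Wilcoxon signed rank test to compare medians", together with McNemar and Bowker tests for paired proportions. It names no covariates. Stage II aims at dose-response relationships for imaging and circulating markers, but the visits it lists are before RT, 6 months and 24 months. Its mixed-model sentence names only echocardiographic, CT and MRI variables. A left/right comparison appears in section 1.7 as a source of preliminary hypotheses.

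CRF CANCER records "Date of the surgery", the axillary procedure and nodal irradiation. Section 9.3 uses none of them.

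**The concern.** A change from baseline can be read as an effect of radiotherapy only if the baseline would otherwise have stayed put. Here the baseline follows an operation by an unstated interval, and the panel in section 3.2.2 includes C-reactive protein, four inflammatory cytokines and nine markers of endothelial activation and dysfunction. If some of these are still raised at baseline, they will drift down with no help from radiation, and the rule counts a fall as readily as a rise. The same drift is subtracted from any true radiation-induced rise. At stake is the selection of markers: the primary objective in section 3.1 is to identify biomarkers of radiation-induced change and carry them into NTCP models.

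**Working it through.** **1. What a paired change contains.** For one marker at visit k, with r0 the mean post-surgical residue at baseline and rk that at visit k:

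expected change = radiation effect − (r0 − rk).

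If the radiation effect is zero and r0 exceeds rk, the expected change is a fall. A paired test without covariates cannot split the two terms.

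**2. Number of pairs.** The plan gives no sample-size figure for the blood endpoint. The 250 in section 9.2 belongs to the echocardiographic endpoint and cannot be reproduced from the stated inputs alone, because within-patient correlation, loss rate, sidedness and the scale of the 2.5% are missing. One reading comes close. A relative 2.5% of 16.5 is 0.4125. With an assumed correlation of 0.5, the SD of the difference is 2.1 × √(2 × 0.5) = 2.1, and n = (2.1 × (1.960 + 0.842) / 0.4125)² ≈ 204. With an assumed 20% loss, 204 / 0.8 = 255. I therefore use 250 × 0.8 = 200 pairs as an assumption, and 250 as the no-loss case.

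**3. Chance of a significant fall with no radiation effect.** Let d be the net residue in SDs of the paired change. Probability ≈ Φ(d√n − 1.96), two-sided 5%. The row d = 0 is the nominal error in either direction.

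| d (assumed) | n = 200 | n = 250 |
|---|---|---|
| 0 | 5% | 5% |
| 0.1 | 29% | 35% |
| 0.2 | 81% | 89% |
| 0.3 | 99% | >99% |

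For n = 200 and d = 0.2: 0.2 × 14.14 − 1.96 = 0.87, and Φ(0.87) ≈ 0.81. The observed drift that just reaches p < 0.05 is 1.96/√200 = 0.139 SD, or 1.96/√250 = 0.124 SD.

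**4. Masking.** A true rise of 0.2 SD would be found with 81% probability at n = 200. With a residue of 0.1 SD the net change is 0.1 and the probability is 29%. With a residue of 0.2 SD the two cancel and 5% remains.

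**5. Check with the planned test.** The Wilcoxon signed rank test was simulated with no radiation effect, 1000 runs per setting. All inputs were assumed: 200 pairs, surgery 4 to 12 weeks before baseline, correlation 0.5, exponential recovery. At 6 months it was significant in 5% of runs with no residue, about 22% with a mean residue of 0.08 SD of the marker, 60% with 0.16, 76% with 0.19 and over 99% with 0.38. At correlation 0.5 the SD of the marker equals that of the paired change, so these agree with step 3. In the same runs, the slope of the 6-month change on a heart dose unrelated to surgery was significant in only about 3% to 6%.

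**6. Where it applies.** The panel names 7 + 4 + 9 + 5 + 21 = 46 markers plus DNA methylation. With three post-baseline visits, that is 46 × 3 = 138 contrasts with the post-surgical baseline. How many involve a marker that responds to surgery cannot be told from the documents.

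**The case against.** The strongest reply is that the plan does not attribute paired changes to radiation. Section 3.2.2 speaks of temporal changes, the paired tests sit in a stage labelled descriptive, and the dose-response question belongs to Stage II, whose aim covers circulating markers. A reader might infer that the plan will declare surgical recovery a radiation effect; the text does not go that far. Step 5 supports the reply in part: recovery unrelated to dose does not bias a dose slope, and it would not bias a left/right contrast either.

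What remains is a gap in the wording. The endpoint is met by a paired change alone and refers to neither safeguard. Stage II omits the end-of-RT visit, where the residue may still be decaying, and does not name blood markers as mixed-model outcomes. The left/right comparison is stated only in the outline. If more extensive axillary surgery goes with nodal irradiation, recovery could also be related to dose, and the dose slope would then need adjustment.

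Two further objections stand. No passage gives the surgery-to-baseline interval or says that any marker is still raised, so zero bias is possible. And surgery is not the only such influence: hormone therapy and its start date are recorded and equally unused in section 9.3. This is a general weakness of a single-arm before/after contrast, which is a reason to rest attribution on dose and not on a surgery covariate alone.

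**Conclusion.** The concern holds as a limitation of the endpoint rule and the Stage I tests. All blood is drawn after surgery, any significant change in either direction counts, and nothing in the rule separates recovery from radiation. Recovery could produce significant falls or hide true rises; the documents do not support saying that it will.

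The percentages are illustrative. They rest on an assumed residue of 0 to 0.3 SD and about 200 assumed pairs. They change little between 200 and 250 pairs, but depend almost wholly on the residue, which is unknown. A reader might also infer that these markers are known to be raised at baseline, or that blood is drawn exactly 1 to 2 weeks before radiotherapy. Neither is stated: the plan groups the markers as inflammatory or endothelial without linking them to surgery, and the 1 to 2 weeks refers to inclusion. The point touches secondary endpoints only, and the repair is cheap enough to be worth making before results are seen.

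**What to change.** In section 3.2.2 (and section 1.4), state that paired changes in blood markers are descriptive, and that a change is called radiation-related only if it is associated with cardiac dose.

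In section 9.3, Stage II:
- name circulating biomarkers as mixed-model outcomes;
- add the end-of-RT sample to the listed visits;
- adjust for days from surgery to the baseline sample, with a visit interaction, and for axillary procedure;
- report the dose association with and without this adjustment.

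The surgery date and axillary procedure are on CRF CANCER; the interval follows from the surgery date and the baseline sampling or visit date. No new visit, sample or patient is needed.

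The cost is modest extra modelling across more than 40 markers, since Stage I has no model to which a covariate could be added. If surgery-to-baseline intervals vary little, the surgery effect will be poorly identified and the adjusted estimates will add little. The dose-association requirement therefore carries the main protection. Its price is that a radiation effect that does not vary over the observed dose range would be reported only descriptively.
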